- Gastrointestinal Symptom questionnaire. Gastrointestinal symptoms will be monitored monthly using the Gastrointestinal Symptom Rating Scale (GSRS). The GSRS is a 15-item questionnaire. Each question has a seven-point Likert-type scale where 1 represents absence of symptoms and 7 represents very troublesome symptoms. The GSRS will be measured monthly.

For Arm 1 only: If the mTBI subject sustains an additional TBI during the study period, the study will be extended for both the mTBI and household control for an additional 6 months. The GSRS will be collected monthly during the 6 month extension.

○

Statistical Considerations

Aim 1a:

In this protocol we intend to compare the GI microbiome of diagnosed mTBI patients against the microbiome of healthy controls (HC). Data will be organized by time (PRE vs. POST) and by treatment (mTBI vs. HC). The hypothesis is that group differences between mTBI and HC will exist at PRE but that GH treatment in the mTBI group will dissolve these differences at POST.

Power calculations using q-PCR data from 22 diagnosed TBI patients and 15 healthy control subjects suggesting that we will be able to detect group differences in genus and/or species in the intestinal flora. These calculations suggest that we would need about 6 subjects per group to have an 80% probability of detecting significant differences in at least one of the previously

identified organisms (two-sided, $\alpha=0.05$). With the proposed subject numbers (25 per group) we calculate that the power would be between 91 – 100 % for at least 8 of the previously identified organisms.

Aim 1b:

Given our recent results from mTBI patients with BIAFAC, that identified two distinct community groups, based upon the presence of specific *Prevotella* species, we require additional participants to achieve group sizes of each type to address differences in the individual species for the pre and post comparisons. Enrollment: We expect to enroll subjects without the need for a HHC to address these differences. These subjects will be compared to matched normal participants from the general population adding 25 TBI and 25 normals to the study creating the power needed to address *Prevotella* positive and negative community types.

[figure not shown]
Aim 2:

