Given the data acquired from two PASC subjects under IRB 20-0361 that have shown indistinguishable profiles to those of BIAFAC communities as well as remarkably reduced GH responses to GST, we expect that the Power calculations explained in this section (above) will also apply to PASC. Because PASC is a recent consequence to the pandemic no data exist to complete Power calculations beyond those of syndromes like BIAFAC that present with similar symptoms. We therefore have proposed enrollment of at least 25 PASC subjects to compare to 25 normal controls already included in this protocol.

For quantifiable (primary) outcomes such as abundances of individual species in the GI microbiome and (secondary) symptom related outcomes, a standard repeated measure ANOVA model will be used. When possible, age and other covariates will be brought into the model to reduce variability and account for random differences between the two groups. Significance tests will be performed at the $\alpha=0.05$ level, and multiple testing corrections will be used to account for potential Type I error rate inflation. Nonparametric, generalized linear, and transformed response models will be considered as necessary to alter the model to account for deviations from standard assumptions (normality, linearity, etc.). Current data support statistical outcomes being established with group sizes similar or slightly larger size than our previous study.

The graph below is based on group difference in *Alistipes onderdonkii*. Power calculations were performed using t-tests with G*Power (two-groups, two-sided, $\alpha=0.05$, Version 3.1.9.2, Germany). Effect size in this case was 1.184.

Below is a list of organisms we identified previously and which were used to conduct the power analyses for the present study. Please note that the intestinal flora includes an incredibly diverse system of organisms and at this time it is difficult to accurately predict which organisms will be included in the biome shifts we expect to see. Therefore, additional organisms may be included in the final microbiome comparisons between mTBI patients and household control subjects. Further power analyses will be conducted using the data collected during this investigation.

Target	n = 20 (10/group)	n=30	n=40	n= 50 (25/group)
Alistipes onderdonkii	70.7%	87.9%	95.4%	98.4%
Desulfovibrio	60.4%	79.3%	89.9%	95.4%
Prevotella spp	97.5%	99.8%	100.0%	100.0%
Akkermansia	64.8%	83.2%	92.6%	96.9%

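### The 91–100% power at 25 per group is for single tests at uncorrected alpha 0.05, not for the multiplicity-corrected species tests that the plan commits to, and Aim 2 relies on the same calculation

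*Combined protocol and SAP*

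**What the plan says.** All of this is in Statistical Considerations unless another section is named.

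- **Aim 1a, pilot basis.** "Power calculations using q-PCR data from 22 diagnosed TBI patients and 15 healthy control subjects" are the source of the effect sizes. The authors add a minimum size: "we would need about 6 subjects per group to have an 80% probability of detecting significant differences in at least one". This refers to the organisms found in their pilot work and is at two-sided alpha 0.05.
- **Aim 1a, power at the planned size.** At 25 per group, "we calculate that the power would be between 91 – 100 % for at least 8 of the previously identified organisms". A table gives power by target (ten taxa and 16s) at 10, 15, 20 and 25 per group.
- **Basis of the table.** "Power calculations were performed using t-tests with" software named as G*Power, for two groups, two-sided, alpha 0.05. The one effect size stated is 1.184, for *Alistipes onderdonkii*.
- **Planned analysis.** For the primary outcomes, which include individual species abundances, "a standard repeated measure ANOVA model will be used". Tests are at alpha 0.05 and "multiple testing corrections will be used to account for potential Type I error rate inflation". No method and no number of tests is given, and the text before the table allows further organisms to be added.
- **Aim 2.** "we expect that the Power calculations explained in this section (above) will also apply to PASC". The size follows from that: "We therefore have proposed enrollment of at least 25 PASC subjects to compare to 25 normal controls already included in this protocol".
- **Enrollment (Experimental Design and Methods).** Arms 1 and 2 together supply 50 mTBI subjects and 50 controls for Aim 1, whereas the Aim 1a power sentence uses 25 per group.

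**The concern.** A power figure should describe the test that will be run. Here the power is for each organism tested alone at 0.05, while the analysis will hold the species tests to a stricter, unstated threshold. A reader of the 91–100% sentence would expect nearly all eight organisms to be declared different if the pilot effects are real. Under the promised correction, that expectation depends on a choice the plan does not make.

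Aim 2 is the most exposed. The transferred calculation is its only sample-size basis, and the plan says that no PASC data exist for another. Specific Aim 2 compares PASC with the arm 2 controls, so the comparison is 25 v 25.

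**Working it through.** **Inputs.** Two-group, two-sided t-test, alpha 0.05, and d = 1.184 for *Alistipes* (Statistical Considerations). For the other ten rows d is not stated. I solved it from the 10-per-group column and checked it against the other three columns.

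**Formula.** With n per group, df = 2n − 2 and noncentrality λ = d√(n/2). Power = P(|T| > t(1 − α/2; df)), where T is noncentral t with parameter λ.

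**Reproducing the plan.** For *Alistipes* at n = 25, λ = 1.184 × √12.5 = 4.186, df = 48 and the critical value is 2.011, giving 98.4%. The same d gives 70.7, 87.9 and 95.4% at 10, 15 and 20 per group, identical to the table. One d per row reproduces all 44 cells within 0.12 point. The table is therefore single-test, uncorrected power.

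**Power under correction at 25 per group, family of 11.** Bonferroni uses α = 0.05/11 = 0.00455 (critical value 2.977) in the same formula. For *Odoribacter*, λ = 0.956 × √12.5 = 3.380, and power falls from 91.2% to 65.5%. Holm and BH were simulated with independent tests (100,000 trials for Holm).

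| Organism | d | Stated (%) | Bonferroni | Holm | BH |
|---|---|---|---|---|---|
| *Prevotella* spp | 1.856 | 100.0 | 100 | 100 | 100 |
| *Alistipes onderdonkii* | 1.184 | 98.4 | 87.9 | 93.9 | 98.0 |
| *Bacteroides vulgatus* | 1.116 | 97.2 | 82.7 | 90.6 | 96.4 |
| *Akkermansia* | 1.106 | 96.9 | 81.8 | 90.0 | 96.3 |
| *Desulfovibrio* | 1.051 | 95.4 | 76.5 | 86.5 | 94.4 |
| *Ruminococcus bicirculans* | 1.012 | 93.9 | 72.2 | 83.4 | 92.6 |
| *Sutterella* | 0.962 | 91.5 | 66.3 | 78.7 | 89.8 |
| *Odoribacter* | 0.956 | 91.2 | 65.5 | 78.4 | 89.6 |
| Number of 8 at 80% or more | | 8 | 4 | 6 | 8 |

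**A wider family under BH.** Assume the added organisms are true nulls and independent. BH power for *Odoribacter* is then about 90% at 11 tests, 83% at 21, 73% at 51 and 63% at 96. The 96 is an assumed upper size, taken from the well count of the qPCR array mentioned in the background.

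**At least one organism at 25 per group.** *Prevotella* alone has about 100% power under Bonferroni over 11 and 99.6% over 96, so this stays near 100% under every correction tried.

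**Aim 1a pooled at 50 per group, family of 11.** The lowest of the eight is 96.7% (Bonferroni), 99.2% (Holm) or 99.7% (BH). This assumes the same effect against household and matched controls.

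**The 6-per-group sentence.** *Prevotella* alone at uncorrected alpha gives 73.0% at 5 and 82.5% at 6 per group, which probably explains the figure (the source is inferred). Compared like for like at 6 per group:

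- *Prevotella* alone goes from 82.5% to about 40% under Bonferroni over 11.
- Any of the 11, if independent, goes from about 99.6% to about 71%.

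**The case against.** **The arithmetic is correct and its basis is disclosed.** This stands. The test, sidedness and alpha are stated and the table has one row per target, so a careful reader can see that it is uncorrected. But the text offers the figures as the power of this study's comparisons, and no figure uses a corrected threshold.

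**The plan's only stated 80% target is at least one organism.** This also stands. A reader might infer that Aim 2 fails its own criterion, or that its power cannot be assessed at all. The documents do not support that: on the at-least-one criterion, 25 per group is ample under every correction considered. What is affected is the claim for eight organisms.

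**False-discovery-rate control would make the loss trivial.** This is true only for a family fixed at the 11 targets, where the loss for *Odoribacter* is under 2 points. The plan names neither BH nor that family, and it allows organisms to be added.

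**Aim 1a may have 50 per group.** If the arms are pooled, there is no shortfall. The Aim 1b paragraph describes arm 2 as additional subjects, so 25 per group may mean arm 1 alone. The Aim 1a shortfall therefore depends on which n is meant.

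**Other uncertainty is larger.** The 95% interval for d = 1.184 from 22 v 15 subjects is 0.46–1.89, or about 36–100% uncorrected power at 25 per group. Carrying TBI effects to PASC on the strength of two subjects is a further leap, which the plan acknowledges. Both points argue for rounded, labelled figures. Neither justifies reporting power at the wrong threshold.

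**Conclusion.** The mismatch is certain: the 91–100% is per-organism power at uncorrected alpha 0.05, and the primary species tests are to be corrected. Its size depends on choices the plan leaves open. At 25 per group over the 11 listed targets, the weakest of the eight organisms loses about 26 points under Bonferroni, 13 under Holm and under 2 under BH. The BH loss grows if null organisms join the family.

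This applies to Aim 2 at 25 v 25, and to Aim 1a only at its stated 25 per group. It does not show a calculation error, and it does not show that the trial is too small to detect any difference.

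The figures rest on effect sizes back-solved from the table, on independence for Holm and BH, and on a t-test approximation to the planned repeated-measures ANOVA. It should be fixed before analysis; the design itself can stand.

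**What to change.** 1. Name the correction method and the family of organisms it covers. State whether organisms added later are inside that family or exploratory.
2. State the analysis n for Aim 1a, reconciling the 25 per group in Statistical Considerations with the 50 and 50 under Enrollment.
3. Replace the 91–100% sentence and the table with power under that method and family, for Aim 2 at 25 v 25 and for Aim 1a at its stated n. Round the figures and label them as a two-sample t-test approximation from pilot effects (22 TBI, 15 controls).
4. At the least, label the existing table as per organism and uncorrected. Print beside it the corrected range for the eight organisms at 25 per group over 11 targets: about 66–100% (Bonferroni), 78–100% (Holm) or 90–100% (BH, for that family only).
5. Label the 6-per-group sentence as uncorrected. If a corrected figure is added, compare the same event on both sides: *Prevotella* alone, or any of the 11.

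The cost is some wording, a recomputed table and a less favourable stated power. No extra patients are needed.

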Title: Brain and Gut Plasticity in mild TBI or post-acute COVID Syndrome Following Growth Hormone Therapy

Principal Investigator: [name]., Internal Medicine, UTMB

Co-I: [name]., Internal Medicine, UTMB

Co-I: [name]., Pediatrics, UTMB

Co-I: E. [name]., Internal Medicine, UTMB

Institution: The University of Texas Medical Branch at Galveston

Sponsors: The Moody Endowment

Sealy & Smith Foundation

Specific Aims

Increasing evidence suggests the gastrointestinal (GI) microbiome is altered in patients with history of mild traumatic brain injury (mTBI). In this project, we propose to characterize the GI microbiome in patients with a history of mTBI or post-acute COVID syndrome complex (PASC) in comparison to healthy controls. Furthermore, we propose to investigate the potential effects of recombinant Human Growth Hormone (rhGH, given as somatropin, a polypeptide hormone (GENOTROPIN)) on the GI microbiome, fatigue, cognition, brain activation, and brain morphology in individuals with a history of mTBI or PASC.

Specific Aim 1a. To characterize the GI microbiome in patients with a history of mTBI compared to controls. - mTBI Baseline vs. Control Baseline - Fecal samples for determination of the GI microbiome will be collected monthly from mTBI subjects and healthy controls over 6 months to examine the diversity of the microbiome within and between groups. **Outcomes:** Genus, species, q-PCR for selected marker organisms.

Specific Aim 1b. To characterize the GI microbiome in patients with a history of mTBI based on presence of *Prevotella spp.* - mTBI *Prevotella spp.* positive Baseline vs. mTBI *Prevotella spp.* negative Baseline - Fecal samples for determination of the GI microbiome will be collected monthly from mTBI subjects over 6 months to examine the diversity of the microbiome within and between groups. **Outcomes:** Genus, species, q-PCR for selected marker organisms

Specific Aim 2. To characterize the GI microbiome in patients with a history of post- COVID-19 syndrome (PASC) compared to arm 2 controls. - PASC Baseline vs. Control Baseline - Fecal samples for determination of the GI microbiome will be collected monthly from PASC subjects over 6 months to examine the diversity of the microbiome within and between groups. **Outcomes:** Genus, species, q-PCR for selected marker organisms.

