Our recent work has shown that cognitive and physical dysfunction are significantly improved with recombinant human growth hormone (rhGH) replacement in patients with abnormal GH secretion. The mechanisms causing fatigue and cognitive dysfunction need to be determined, but our brain imaging from functional MRI (fMRI) data suggests that brain connectivity is impaired in patients and rhGH may improve connectivity. In chronic TBI patients who have received rhGH treatments, it is not yet established if the GI microbiome is returned to a healthy profile observed in control cohorts. Our *overall hypothesis* is that baseline GI microbiome in mTBI will be significantly altered compared to household controls, and that rhGH therapy may result in symptom resolution in mTBI which may correlate with the change in GI microbiome.

Post-acute COVID Syndrome Complex (PASC)

The onset of the COVID-19 pandemic has led to a subset of patients that, once recovered from the acute infection, also experience an intractable and debilitating set of lingering symptoms termed post-COVID syndrome (PASC). The most common symptoms include anxiety, shortness of breath, continued loss of the sense of smell and taste, loss of appetite with subsequent weight loss, sleep difficulties, severe fatigue, cognitive dysfunction (foggy brain) and increased frailty. These patients frequently present to the emergency room looking for symptom management because they are unable to perform normal activities of daily living and maintain job performance. The mechanisms behind this syndrome have proven elusive because patients varied in symptom severity and treatment regimen including different requirements for hospitalization, supplemental oxygen, dexamethasone and remdesivir.

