Odoribacter	52.5%	71.5%	83.8%	91.2%
Ruminococcus bicirculans	57.2%	76.3%	87.7%	93.9%
Bacteroides vulgatus	65.6%	83.9%	93.1%	97.2%
Sutterella	53.0%	72.0%	84.2%	91.5%
Lachnoclostridium	30.8%	44.4%	56.4%	66.4%
Streptococcus salivarius	27.8%	40.2%	51.4%	61.2%
16s	6.8%	7.8%	8.8%	9.8%

Study Timeline

Interventional, mechanistic studies such as this one are routinely performed by our research group and involve fine coordination between our team and the Clinical Research Center at UTMB. From experience, we know that we will be able to complete ~16 experiments of this type of trial per year. Thus, we anticipate completing all patients at the end of year 3. Therefore, a 3-year span is needed to accomplish all aims, and data analysis and manuscript writing will follow.

Protection of Human Subjects

A. Risks to Human Subjects

Human subject involvement and characteristics. Arm 1: We propose to study a total of 50 patients both males and females, with a history of mild TBI (n=25) ages 18 to 70 and their household controls (n=25) ages 18 and up. As the mTBI subjects will be selected for study based on their history and symptom complex, we expect that screening failures will be low (approximately 20). We also expect approximately 4 sets (8 total) of subjects to drop out during the course of the study. Thus, in order to achieve a total of 25 pairs (50 individuals) completing the study, we anticipate screening and enrolling approximately 78, but up to 100 individuals over 3 years. Arm 2: We propose to study a total of 50 patients both male and female consisting of patients with a history of mild TBI (n=25) and healthy matched controls (n=25), ages 18-70. As the mTBI subjects will be selected for study based on their history and symptom complex, we expect that screening failures will be low. Arm

3: We propose to study a total of 25 patients both male and female consisting of patients with a history of COVID-19 ages 18 – 70. As PASC subjects will be selected for the study based on their history and symptom complex, we expect that screening failures will be low.

ARM 1:

1. mTBI Inclusion criteria Male or female with a diagnosis of mild TBI.
2. At least 6-month post-injury.
3. Ages 18 to 70 years.
4. Lives in same household as paired control that meets inclusion/exclusion criteria.
5. Participant is willing and able to give informed consent for participation in the study.

mTBI Exclusion criteria

1. Unable to walk unassisted.

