2. Significant heart, liver, kidney, blood or respiratory disease.
3. History of chest pain or coronary heart disease.
4. Uncontrolled Diabetes mellitus.
5. Any history of a recently (12 months) diagnosed cancer other than a skin cancer (excluding melanoma).
6. Current alcohol or drug abuse.
7. Premorbid history of psychiatric disorder.
8. Premorbid history of head trauma.
9. Pregnancy or become pregnant during the trial.
10. Subjects who are deficient in cortisol or thyroid at screening will be excluded until hormone abnormalities have been corrected.
11. Subjects with chronic pain who are being managed with narcotics will be excluded as the effects of central nervous system depressants may interfere with study test results.
12. Subjects with a history of inflammatory bowel disease, Celiac disease or active diverticular disease.
13. Subjects with MRI incompatible devices.
14. Subjects with severe claustrophobia.
15. Other medical condition or medication administration deemed exclusionary by the study investigators.

Household Control Inclusion criteria

1. Ages 18 and up.
2. Lives in same household as paired mTBI subject that meets inclusion/exclusion criteria.
3. Participant is willing and able to give informed consent for participation in the study.

Household Control Exclusion criteria

1. Significant heart, liver, kidney, blood or respiratory disease.
2. Uncontrolled Diabetes mellitus.
3. Any history of a recently (12 months) diagnosed cancer other than a skin cancer (excluding melanoma).
4. Current alcohol or drug abuse.
5. Premorbid history of psychiatric disorder.
6. Premorbid history of head trauma.

7. Pregnancy or become pregnant during the trial.
8. Subjects who are deficient in thyroid at screening will be excluded until thyroid hormone is replaced.
9. Subjects with a history of inflammatory bowel disease, Celiac disease or active diverticular disease.
10. Other medical condition or medication administration deemed exclusionary by the study investigators.

ARM 2:

mTBI Inclusion criteria

1. Male or female with a diagnosis of mild TBI.
2. At least 6-month post-injury.
3. Ages 18 to 70 years.
4. Participant is willing and able to give informed consent for participation in the study.

mTBI Exclusion criteria

1. Unable to walk unassisted.
2. Significant heart, liver, kidney, blood or respiratory disease.
3. History of chest pain or coronary heart disease.
4. Uncontrolled Diabetes mellitus.

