- d. To minimize the possibility of coercion or undue influence all subjects will be given a copy of the approved consent forms and encouraged to discuss with their families prior to meeting the coordinator for the consenting process. The study team will be make it very clear to the potential mTBI participants that to meet inclusion criteria for this study, they must have an eligible household partner. If either one of the pair withdraws consent or is terminated, the other will be terminated by the study team.
- e. We are requesting an alteration of the consenting process so that we can obtain written consent and perform the medical screening in the same visit. The medical screening requires an overnight fast, which the IRB deems as research. Subjects will be provided a copy of the approved consent form for their review prior to their consenting/screening visit. The risk involved is an overnight fast. An overnight fast for medical tests is routine for medical care and would not require consent outside the scope of research. When subject arrives at CRC for the screening visit, the study team will begin with the consenting process as described above. We are only requesting the waiver of written consent for fasting to occur during the consenting visit. Written consent would be obtained prior to any study related procedures.

Recruitment Methods and Consenting Process (Arm 2)

- a. Potential mTBI subjects may be patients of the investigators.
- b. mTBI subjects will be recruited through ads and flyers around the community as well as in [name] Medicine Endocrinology clinic. The study will also be listed on the UTMB

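### Arm 1 is recruited as 1:1 household pairs, but the mTBI-versus-household-control comparison is powered as two independent groups and the named model has no household term, which costs precision if partners are alike

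*Combined protocol and SAP*

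**What the plan says.** **Design.** In Arm 1 a control is recruited for each mTBI patient (Figure 1 legend). The Household Control Inclusion criteria require that the control "Lives in same household as paired mTBI subject that meets inclusion/exclusion criteria", and the mTBI criteria mirror this. The target under Human subject involvement and characteristics is set "in order to achieve a total of 25 pairs (50 individuals) completing the study". Under Recruitment Methods and Consenting Process (Arm 1), "If either one of the pair withdraws consent or is terminated, the other will be terminated by the study team"; Stopping Rules also tie the two members together.

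**Question.** The overall hypothesis in Background and Significance is that "baseline GI microbiome in mTBI will be significantly altered compared to household controls". Specific Aim 1a is labelled "mTBI Baseline vs. Control Baseline". Statistical Considerations adds that "additional organisms may be included in the final microbiome comparisons between mTBI patients and household control subjects".

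**Power.** "Power calculations were performed using t-tests with G*Power (two-groups, two-sided", alpha 0.05), with an effect size of 1.184 for Alistipes onderdonkii. Under Aim 1a the stated size is 25 per group, with 91 to 100% power for at least 8 organisms.

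**Analysis.** Aim 1a arranges the data by time (PRE, POST) and group (mTBI, healthy control). For quantifiable outcomes, "a standard repeated measure ANOVA model will be used", with age and unnamed other covariates where possible and a multiplicity correction that is not named. Alternative models are allowed for departures from assumptions such as normality and linearity.

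**Which arms.** Enrollment assigns mTBI subjects from Arms 1 and 2 to Aims 1a and 1b (50 in total) and controls from both arms to Aim 1 (50 in total). Whether Aim 1a is analysed in Arm 1 alone or pooled is therefore not settled.

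**The concern.** Repeated-measures ANOVA by group and time handles correlation between two visits of the same person. It does not handle correlation between two people in the same home. Shared diet and environment make a positive correlation plausible for gut organisms, and removing that shared variation is the usual statistical reason to choose household controls.

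The trial pays for the pairing. Each patient needs a willing, eligible housemate, and losing one person removes two (about 4 sets, 8 people, are expected to drop out). As written, no specified analysis recovers the benefit. What is at stake is the precision of the month 0 and month 6 group differences, mainly for organisms where the plan's own power is modest. Leaving the choice between a paired and an unpaired analysis until the data are in hand would also be undesirable.

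**Working it through.** **1. The plan's own power.** Inputs: d = 1.184, two-sided alpha 0.05, n = 10, 15, 20, 25 per group. Two-sample t-test: df = 2n − 2, noncentrality d√(n/2). Result: 70.7, 87.9, 95.4 and 98.4%, exactly the Alistipes row. Treating 1.184 as a paired effect size gives 91.4, 98.9, 99.9 and 100.0%, which does not match. The table is therefore an independent-groups calculation, and its arithmetic is correct.

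**2. Effect sizes for weaker rows.** Back-solving the 25-per-group column with the same formula: Odoribacter (91.2%) d = 0.956; Lachnoclostridium (66.4%) d = 0.688; Streptococcus salivarius (61.2%) d = 0.648.

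**3. Standard error of the PRE (or POST) difference, in SD units.** The within-pair correlation rho is assumed.

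- Arm 1 alone, 25 pairs: the unpaired formula gives √(2/25) = 0.283; the true value is √(2(1 − rho)/25). Ratio = 1/√(1 − rho).
- Pooled, 50 per group with 25 pairs among them: the unpaired variance is 2/50 = 0.04. The pairs reduce the true variance by 2 × 25 × rho/50² = 0.02·rho. Ratio = √(0.04/(0.04 − 0.02·rho)).

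| rho | 25 pairs: true SE | SE too large by | size of nominal 5% test | independent n per group matched by 25 pairs, 25/(1 − rho) | pooled: SE too large by |
|---|---|---|---|---|---|
| 0.1 | 0.268 | 5% | about 4% | 28 | 3% |
| 0.2 | 0.253 | 12% | about 3% | 31 | 5% |
| 0.3 | 0.237 | 20% | about 2% | 36 | 8% |

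The size column is the simulated rejection rate of the unpaired t-test on 25 correlated pairs with no true difference.

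**4. Power at 25 pairs, rho 0.3, alpha 0.05.** Paired test: df = 24, noncentrality d√(25/(2(1 − rho))) = d × 5/√1.4. Unpaired power on the same correlated pairs comes from simulation.

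| Organism | noncentrality | unpaired | paired |
|---|---|---|---|
| Lachnoclostridium | 0.688 × 5/1.183 = 2.91 | about 69% | about 80% |
| S. salivarius | 0.648 × 5/1.183 = 2.74 | about 63% | about 75% |
| Odoribacter | 0.956 × 5/1.183 = 4.04 | about 94–95% | about 97% |

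**5. Power when pooled.** At 50 per group and rho 0, the two-sample formula already gives 92.6% for Lachnoclostridium, 89.4% for S. salivarius and 99.7% for Odoribacter. At rho 0.3, using the pairing moves Lachnoclostridium from about 94 to 96%.

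**6. Group-by-time.** Write each value as household effect + subject effect + visit residual. POST minus PRE removes the first two if the household effect is constant over time. With an assumed retest correlation of 0.5, the residual variance is 0.5, each change has variance 2 × 0.5 = 1, and the difference in mean change has SE √(2 × 1/25) = 0.283 at every rho, the same as the unpaired formula. Nothing is lost on this contrast.

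**7. Price of pairing if rho is zero (25 pairs).** The noncentrality is unchanged, but df falls from 48 to 24. At alpha 0.05: Odoribacter 91.2 to 90.0%, Lachnoclostridium 66.4 to 64.6%, S. salivarius 61.2 to 59.4%. At an assumed 0.05/11 (the table has 11 rows): 65.6 to 60.3%, 30.6 to 27.2% and 26.0 to 23.1%. At alpha 0.05 the paired test overtakes the stated figures once rho passes about 0.04; for Odoribacter at 0.05/11, break-even is at or just below 0.1. Pooled, the loss at alpha 0.05 is about 1 point or less.

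**The case against.** The strongest reply is that no stated conclusion is wrong. The power claim covers eight organisms at 91% or more; it is correct for the test named and is not overstated when rho is zero or above. The larger gains fall on two organisms outside that claim, and only if Aim 1a is Arm 1 alone. On the pooled reading that Enrollment allows, half the controls share no household with a patient and the gain is small. Rho is unknown: household controls need only be adults in the same home and are not matched on age or sex. The pilot (22 patients, 15 controls) was not a 1:1 paired set, so nothing shows that a within-pair correlation was available for planning. All of this stands, and it limits the weight of the point.

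It is also true that the open list of covariates and the promised further power analyses do not exclude a household term. A reader might infer that the plan rules one out; it does not. It specifies none, and the listed fallbacks concern normality and linearity, not dependence between partners.

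Other stronger readings are not supported:

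- **Inflated false positives.** This needs negative rho (at −0.1 the size is about 6.1%), and nothing in the documents suggests it.
- **A large gain from very high rho.** Rho of 0.5 with a retest correlation of 0.5 would leave no subject variance: people would resemble their partners as much as themselves six months later.
- **Loss of significance at POST read as normalisation.** Aim 1a does predict that PRE differences vanish at POST, but no passage adopts that decision rule. The planned layout already contains a group-by-time test, and a multiplicity correction is promised.

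**Conclusion.** The point holds as a mismatch between design and analysis. Arm 1 is paired, the power calculation treats the groups as independent, and the named model has no household term. With positive rho, the unpaired analysis of the PRE or POST group difference is conservative.

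Its size depends on which arms Aim 1a uses. For rho between 0.1 and 0.3, the standard error is about 3 to 8% too large if the arms are pooled at 50 per group, and 5 to 20% too large for 25 Arm 1 pairs. In the latter case the power at stake at rho 0.3 is about 11 to 12 points for Lachnoclostridium and S. salivarius, and about 2 to 3 points for Odoribacter.

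These figures rest on an assumed rho, equal variances, effect sizes back-solved from the plan's table and, unless stated, uncorrected alpha 0.05. The treatment-related contrast, group by time, is untouched if the household effect is stable over time. This is a cheap improvement that should be made before analysis. It does not invalidate the planned test.

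**What to change.** In Statistical Considerations, state for Aim 1a:

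- Whether the analysis uses Arm 1 alone or Arms 1 and 2 pooled.
- A linear mixed model with group, time and group-by-time (plus arm if pooled), a subject effect, and a household effect for Arm 1 pairs. For Arm 1 at PRE alone, a paired t-test is the simple equivalent.
- That the household effect sharpens the PRE and POST group comparisons and cancels from group-by-time.
- That the promised further power analyses will use the observed within-pair correlation.

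The cost is wording and a standard model; no new subjects, visits or samples are needed. The statistical downside arises if rho is near zero: with 25 pairs, about 1 to 2 points of power at alpha 0.05 and about 3 to 5 points at an assumed 0.05/11. If pooled, the loss at alpha 0.05 is about 1 point or less.
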